#### Cost Data

Cost data will be analysed using parametric and non-parametric statistical methods which explicitly allow for the censoring of (indirect & total) costs at 28 days, i.e. for those patients who are not discharged from hospital within 28 days and thus enable an unbiased assessment of potential cost differences between the three diagnostic groups to be made. Estimation of the cost distribution over longer timescales will make use of extrapolation techniques using time of discharge obtained from hospital information systems.

	Study Day			
	Admission	Days	Day 28	
Assessments	(Day 1)	2, 3, 4, 7 ( + 1), & 10 ( + 1)	( + 2)	
Pre-study assessment by admitting medical team	✓			
Note time of admission (CRF)	$\checkmark$			
Inclusion/Exclusion criteria check (CRF)	~			
Written informed Consent (or Assent) (CRF)	~	✓ (Consent upon recovery)		
Demography/immunisation status check (CRF)	~			
Medical history/concomitant medications check (CRF)	~			
Symptom assessment (CRF)	~			
Clinical findings, including body weight and temperature (CRF). Establish when patient first becomes apyrexial ( $\leq$ 37.2°C), requires supplemental O 2 , and remains so for >24 hours (CRF)	1	✓ (temperature, O 2 )		
EuroQol. Quality of Life assessment (CRF)				
MRC Dyspnoea Scale	~			
Physical Activity Questionnaire		✓		
Diagnostic studies ordered by the admitting medical team (CRF)	~	$\checkmark$		
Collection of trial specific diagnostic specimens (CRF):	~	✓ (antibody, Day 10- 90)		
Nasopharyngeal (Quidel & virus culture) Nasopharyngeal Swabs Sputum (Gram stain & culture) Urine (Binax NOW) Blood (Blood cultures, serum antibodies)		Day 2-3 if first swabs positive if available.		
Record time when diagnostic test results were made available to the ward nurses, and/or admitting team (CRF)	~	4		
Record antimicrobials & antivirals (identity,route, dose, time of administration) prescribed by admitting medical team (CRF)	~			
Note the time of any changes in antimicrobials & antivirals (identity,route, dose, time of administration) prescribed by admitting medical team (CRF)		1		
Bed location, i.e., record bay or a single room (CRF)	~			
Note time of any subsequent change in isolation status (CRF)		$\checkmark$		
ITU and ventilatory support: Document whether admitted or required ventilatory support (CRF)	~	¥		
Date of hospital discharge/ Death within 28 days of admission (CRF)		✓		
Discharge diagnosis (CRF)		✓		

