#### 5.2 Inclusion criteria

Men or women must satisfy the following to qualify for enrolment:

- Able and willing to give written informed consent, OR a relative or carer is able and willing to give informed Assent, OR in the event that Informed Consent or Informed Assent cannot be obtained from the patient or carer (either because: (a) the patient is so sick (breathless or confused) that he/she is temporally unable to assimilate information regarding the study to judge whether to participate; or (b) the patient has pre-senile or senile dementia) f the following are satisfied:
  - (i) The patient provides written informed consent after reading the synopsis of the Patient Information Leaflet (Appendix IVa). In such cases the patient must be asked to provide Informed Consent after perusal of the 'Full' Information Leaflet when he/she is sufficiently well to do so;
- Age ≥65 years, OR age ≥18-64 years with underlying chronic heart or lung disease including asthma, or pneumonia / influenza type symptoms.
- Have an *acute exacerbation* of chronic cardio-pulmonary illness of ≤168 hours (7 days) duration, OR an *acute cardio-pulmonary illness* or influenza-like illness of ≤7 days duration, including:
  - Pneumonia\*,
  - Influenza/influenza-like illness\*,
  - Exacerbations of chronic obstructive pulmonary disease (COPD)\*,
  - Bronchitis\*,
  - Asthma\*,
  - Congestive heart failure\*, Cardiac arrhythmia\*.
- Can be recruited to the study within a 16-hour period of initial assessment by an on-call doctor on the Medical Admissions Unit, or another ward accepting acute medical admissions,
- Able and willing to adhere to the procedures stated in the protocol
- Patients should have access to a telephone.

\*NOTE: these are provisional or suspected clinical diagnoses that have been made either by the referring general medical practitioner or by the admitting medical team in the differential diagnosis. In general, it is expected that participants will have at least one respiratory symptom and one systemic symptom,  $OR \ge 2$  respiratory symptoms from at least two of the following bullet points, including:

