#### 6.2.6 Supplemental oxygen and CPAP (Days 2, 3, 4, 7, 10)

The study nurse will record in the CRF whether the study participant required supplemental oxygen (and CPAP) during days 1-10 of admission, and when supplemental oxygen (and CPAP) was no longer necessary (i.e., not required for a period of at least 24 hours).

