two-thirds are admitted during the period 09:00-21:00h, which reduces the pool of eligible subjects to 3669 (2/3 x 5504). We estimate that three-quarters of those who are invited to participate will do so (we carried out a study of respiratory virus infections in children at the Leicester Royal Infirmary; the parents of 86% agreed to participate). On the basis of these observations, we estimate that 2752 (3/4 x 3669) eligible elderly people could be recruited. Thus we anticipate recruiting a similar number of elderly patients as in the study by Falsey *et al*, which was carried out in Rochester and Syracuse hospitals over three winters.

On the basis of pneumonia admissions data for the elderly ( $\geq 65$  years) for the period September 1 – 30 April, 2002/3 and 2003/4 (when 1354 case were admitted over 485 days), we expect that 664 of an expected 1859 pneumonia (J12.9-J18.9) admissions will be recruited. Similarly we expect to recruit 556 participants with unspecified acute lower respiratory tract infections (J22.X), 683 with chronic obstructive pulmonary disease, and 735 participants with 'heart failure'.

The number of high-risk patients aged 18-64 years has not been factored into the above estimates. We have not been able to obtain historical data on the number of admissions among 18-64-year-olds to UHL hospitals who have underlying 'high-risk' medical conditions. However, by examining recent national data for admissions for comparable age groups, and making assumptions about the proportion of patients who have underlying high-risk conditions, we estimate that an additional 83 cases of pneumonia, 93 cases of unspecified acute lower respiratory tract infections, and 181 cases of COPD could be recruited.

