#### 7.5.1 Clinical endpoints

- 1. Impact of test result on prescribing, specifically:-
  - (a) Time, from admission to MAU, to first administration of 'narrow-spectrum' antibiotics, for patients in Groups 1, 2, and 3, who are prescribed antibiotics.
  - (b) Time, from admission to MAU, to first administration of oral antibiotics, for patients in Groups 1, 2, and 3, who are prescribed antibiotics
  - (c) Time (hours) from admission to MAU to prescription of 'no antibiotics' (oral or intravenous) administered to patients in Groups 1, 2, and 3, who have influenza or RSV.
  - (d) Proportion of patients with influenza in Groups 1, 2, and 3 who are prescribed neuraminidase inhibitors.
- 2. Clinical outcomes, specifically:-
  - (a) *Length of hospital stay* until discharge:
    First, for all patients in Groups 1, 2, and 3.
    Second, for all patients with (i) influenza; (ii) RSV; and (iii) *S. pneumoniae* infection in Groups 1, 2, and 3.
  - (b) Fever duration (during the first 10 days of hospitalisation) Time from admission (hours) until the patient first became apyrexial (temperature ≤37.2°C), and remained so for a period of at least 24 hours:

First, in all patients in Groups 1, and 2 in comparison to Group 3.

Second, in patients with S. pneumoniae in Groups 1, and 2, in comparison to Group 3.

(c) Supplemental oxygen dependence and CPAP dependence (during the first 10 days of hospitalisation) Times from admission (hours) until the patient required (i) no supplemental oxygen, and (ii) no CPAP, for a period of at least 24 hours: First, in all patients in Groups 1, and 2 in comparison to Group 3.

Second, in patients with S. pneumoniae in Groups 1, and 2, in comparison to Group 3.

- (d) Admissions to Intensive Care (during the first 10 days of hospitalisation):
  First, the proportion of patients with *S. pneumoniae* infection in Groups 1, 2, and 3.
  Second, to better define the burden of influenza and RSV, the proportion of all patients with (i) influenza, and (ii) RSV who require ITU support.
- (e) *Ventilatory support* (during the first 10 days of hospitalisation):
   First, the proportion of patients with *S. pneumoniae* infection in Groups 1, 2, and 3.
   Second, to better define the burden of influenza and RSV, the proportion of all patients with (i) influenza and (ii) RSV who require ventilatory support.
- (f) *Deaths* (within 28 days of hospitalisation):

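### Fever, oxygen and CPAP durations are compared in populations not limited to patients who had the problem at entry, which dilutes the contrast towards no difference; separately, one schedule row states the opposite oxygen event

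*Protocol*

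**What the plan says.** Section 7.5.1 defines fever duration as "Time from admission (hours) until the patient first became apyrexial (temperature ≤37.2°C), and remained so for a period of at least 24 hours" and oxygen and CPAP dependence as "Times from admission (hours) until the patient required (i) no supplemental oxygen, and (ii) no CPAP, for a period of at least 24 hours", both over the first 10 days. Each is compared in two populations: "First, in all patients in Groups 1, and 2 in comparison to Group 3", then "Second, in patients with S. pneumoniae in Groups 1, and 2, in comparison to Group 3". The synopsis endpoints repeat this.

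Section 5.2 admits pneumonia and influenza-like illness, and also COPD exacerbation, asthma, heart failure and arrhythmia. On symptoms it states only an expectation: "In general, it is expected that participants will have at least one respiratory symptom and one systemic symptom". Feverishness is one of several systemic symptoms that could satisfy it; oxygen and CPAP are not entry conditions. Section 7.1 expects, among the elderly recruits, "683 with chronic obstructive pulmonary disease, and 735 participants with 'heart failure".

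No passage says what duration is given to a patient who arrives apyrexial, off oxygen or off CPAP. By contrast, items 1(a) and 1(b) of the same section are limited to patients prescribed antibiotics.

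On recording, section 6.2.6 asks the nurse to note "whether the study participant required supplemental oxygen (and CPAP) during days 1-10 of admission" and when it was no longer necessary. The schedule of assessments table instead asks when the patient first "requires supplemental O 2 , and remains so for >24 hours (CRF".

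**The concern.** A duration of fever, oxygen or CPAP carries information about recovery only in patients who have the problem. If everyone is included, part of what is compared is the share who arrived with it, which the test result cannot change.

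This matters because of the conclusion that these endpoints support. Objective 7 in section 2.1 carries the hypothesis that streamlining antimicrobials does not worsen outcome, and section 1.11 makes absence of added morbidity a condition for adopting the tests. Dilution towards no difference is conservative for a claim of benefit, but it favours a claim of no harm. Sections 3.5 and 10.4 name the feared harm: narrowing of therapy in an unrecognised mixed infection. Slower recovery from such harm would be expected to show mainly in patients who were febrile or needing oxygen.

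The schedule row is a separate matter. Taken literally, it captures the start of sustained oxygen need, while the endpoint is its end.

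**Working it through.** **No figure to reproduce.** Section 7.4 gives power only for diagnostic accuracy, length of stay and isolation. It gives no effect, spread or prevalence for these three durations.

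**Inputs from the protocol.** 2752 elderly patients, 20% dropout, three groups (sections 7.1 and 7.4): 2752 × 0.8 / 3 = 733.9, about 734 per arm.

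Case mix (section 7.1): COPD plus heart failure = (683 + 735) / 2752 = 1418 / 2752 = 51.5%; pneumonia = 664 / 2752 = 24.1%. This makes a sizeable non-febrile share plausible. It does not establish one, and it says little about oxygen need.

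**Assumptions.** A share f has the problem at entry. Their control-arm duration is exponential with mean 48 h, capped at 240 h (the 10-day window). All other patients are given 0. The test is two-sided at 5%. None of these is in the protocol apart from the window.

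**Dilution of the mean.** All-patient difference = f × difference in affected patients. A 30% shorter duration is 0.3 × 48 = 14.4 h before the cap. Over all patients that becomes 0.3 × 14.4 = 4.3 h at f = 30%, and 0.2 × 14.4 = 2.9 h at f = 20%.

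**Simulated power, 30% shorter duration in affected patients:**

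| Share affected | All patients, rank test | All patients, log-rank or t-test | Affected only |
|---|---|---|---|
| 20% | about 6% | about 57% | 73-83% |
| 30% | about 8% | about 80% | 91-97% |

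In the last column the lower value is the rank test and the upper the log-rank test. Independent repeats agree to within a few percentage points. At f = 50% they give 31-36% by rank test and 97% by log-rank in all patients, against 98-99% in affected patients. At f = 5%, a share that might suit CPAP, they give 3-5% by rank test and 14% by log-rank in all patients, and only 22-29% in affected patients.

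**A smaller effect (resolution 1.25 times faster):**

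| Share affected | All patients, rank test | All patients, t-test | Affected only, rank test |
|---|---|---|---|
| 20% | 5% | 31% | 41% |
| 50% | 17% | 67% | 75% |
| 70% | 47% | 86% | 87% |

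The rank test suffers most because the block of tied zeros dominates the ranking. Log-rank and mean comparisons lose less, and at high shares almost nothing.

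**Schedule row.** The synopsis follow-up list, section 6.2.6 and item 2(c) of section 7.5.1 all record when oxygen was no longer needed. The table row runs fever and oxygen together in one sentence, so its wording for oxygen becomes the onset of need.

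**The case against.** The strongest reply is that the collapse in power comes from choosing a rank test. The protocol names no test for these durations. For its other times from admission (prescribing, isolation) it uses survival methods, and with those most of the power survives. This stands, and it rules out saying that the comparison cannot show an effect. A rank test is still a realistic possibility, since section 7.6 starts with non-parametric comparisons for length of stay, quality of life and speed of tests.

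A reader might also infer that most values are zero. The protocol does not support that: it gives no prevalence and does not code unaffected patients as zero. A majority without the problem is plausible for CPAP, uncertain for fever and doubtful for oxygen in acute cardio-pulmonary admissions.

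The all-patient contrast is a valid randomised comparison of testing policies and fits the intention-to-treat statement in section 7.6. That stands too, and is why it should stay. The pneumococcal population sits closer to the feared harm, but it is not limited to affected patients either. The death reporting and data monitoring route in section 10.4 is a separate safeguard; it does not measure recovery time.

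Coding rules and tests may be in an analysis plan that is not shown, so their absence is not the point. The two populations are fixed in the protocol.

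Patients on long-term home oxygen might never reach the oxygen event. The protocol does not mention them. They would add noise equally across randomised arms, so this is secondary and not a demonstrated error.

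On the schedule row, section 6.2.6 is the operative instruction and is clear. It does not follow that nurses would record the wrong event, only that the documents disagree.

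**Conclusion.** The point holds as one of dilution. Both stated populations for fever, oxygen and CPAP duration include patients who never had the problem, and the resulting pull towards no difference favours the no-harm hypothesis. Under the assumed 48 h mean and 30% shorter duration, with 20-30% affected, the loss is moderate by log-rank or t-test (57-80% power against 73-97% in affected patients) and near total by rank test (6-8%). It shrinks as the share affected rises. The shares, mean, effect and zero coding are all assumptions, so the true size is unknown. For a rarely used support such as CPAP, even the affected-only comparison would have low power. These are not powered endpoints, but a null result on them would be cited as reassurance about recovery.

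The contradiction over the oxygen event between the schedule table and the other passages is established from the text alone.

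**What to change.** In section 7.5.1, items 2(b) and 2(c), and the synopsis:

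- Keep the all-patient comparison as the intention-to-treat contrast, and state the value given to a patient without the problem at entry.
- Add, for each duration, a comparison in patients who had the problem before allocation: temperature above 37.2°C, on supplemental oxygen, or on CPAP, as recorded at or before randomisation.
- Do not define this subset by need at any time during days 1-10. That is partly post-randomisation and could differ by arm.

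Reconcile the oxygen wording in the schedule table with the synopsis follow-up list and sections 6.2.6 and 7.5.1.

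The cost is small. Entry temperature is already recorded (section 6.1.9), and oxygen and CPAP need are tracked from day 1 (section 6.2.6); the form should let status at or before randomisation be told apart from later need. The added comparison has a smaller denominator, and fever or oxygen need that begins after randomisation is captured only in the all-patient comparison. Recruitment may follow initial assessment by up to 16 hours, so some problems will resolve before allocation. Counting any record at or before randomisation keeps those patients in, at the price of some noise common to all arms.

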#### 7.5.2 Financial endpoints

- 1. Costs of diagnostic tests, Costs will be identified for:
  - (a) Rapid near patient test for influenza (Quidel);
  - (b) Rapid near patient test for pneumococcus (Binax NOW),
  - (c) Molecular (multiplex PCR) tests for influenza A and B and RSV A and B
  - (d) 'Prompt' antigen detection test for pneumococcus (Binax NOW), using x25 concentrated urine in the laboratory
  - (e) Culture (blood and sputum) for S. pneumoniae
  - (f) Gram staining of sputum samples
  - (g) Cell culture for influenza A and B
  - (h) Cell culture for RSV A and B
  - (i) Other tests that may be applied, eg immunofluorescence
- 2. Care costs Cost of inpatient stay ( $\pm$  95%CI) will be determined for:
  - (a) All patients in Groups 1, 2, and 3;
  - (b) All patients (in all groups) with (i) influenza, (ii) RSV, and (iii) S. pneumoniae infection, and
  - (c) Patients with (i) influenza, (ii) RSV, and (iii) S. pneumoniae infection in Groups 1, 2, and 3.

For patients who are discharged within 28 days of admission, health care resource use in the period after discharge will be recorded using a simple questionnaire administered in a telephone interview.

- 3. Cost-savings that accrue from earlier use of narrow-spectrum antibiotics, oral therapy, or avoidance, or discontinuation of antibiotics will be assessed in
  - (a) All patients in Groups 1, 2, and 3;
  - (b) Patients with (i) influenza, (ii) RSV, and (iii) S. pneumoniae infection in Groups 1, 2, and 3,
- 4. Economic evaluation of near patient and rapid molecular diagnostic tests will be assessed by two main outcomes measures
  - (a) Cost per case detected,
  - (b) Cost per QALY

#### 7.5.3 Endpoints for laboratory assessment of diagnostic tests

- 1. Diagnostic accuracy,
  - (a) Sensitivity,

- (b) Specificity
- (c) Positive predictive value,
- (d) Negative predictive value, and
- (e) Discrepant analysis of near patient and molecular diagnostic tests,

will be estimated in comparison with traditional and other (e.g., serology) laboratory tests.

#### 2. Ease of use of rapid near patient and molecular tests

Molecular, near patient, and traditional laboratory culture diagnostic tests will scored independently for ease of use by three investigators, in terms of whether they can be done:

- (a) On site,
- (b) Require special laboratory facilities,
- (c) Require special equipment,
- (d) The number of reagents required,
- (e) The number of steps and total benchtime,
- (f) Ease of disposal/decontamination of used equipment and reagents,
- (g) Technical competency required of the operator,
- (h) Training period required to reliably carry out the test, and any
- (i) Health and safety implications

#### 3. Speed of tests,

Will be assessed in terms of the median time from specimen collection to result:

- (a) Appearing in the case-notes
- (b) Appearing on Pathology Department results' database (APEX),
- (c) Being phoned to the ward
- (d) Being acted upon in comparison to traditional laboratory culture.

Speed of tests will be determined for -

- (i) All patients in Groups 1, 2, and 3;
- (ii) Patients with influenza; RSV, and S. pneumoniae infection in Groups 1, 2, and 3,
- (iii) Pneumococcal immnunity: Levels of anti-pneumolysin, anti-neuraminidase, and 1gG antibody in sera and anti-neuraminidase induced CD4 T cell activation and proliferation profiles from CD4 cells collected from peripheral blood will be compared in subjects with and without pneumococcal infection.

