#### **1.6** Diagnostic tests for influenza

Viral isolation and haemagglutination inhibition antibody testing are standard methods for influenza diagnosis, but have drawbacks. Virus isolation by culture from respiratory secretions may take a week or

more (a median of 8 days in one recent study); it requires specialised laboratory facilities; and does not provide results that could influence the initiation of treatment. Serology provides a retrospective diagnosis. Neither test alone is considered a 'gold standard' for influenza diagnosis, since each lacks sensitivity, but culture and serology together have been used as 'gold standard' to assess molecular diagnosis.

Tests for rapid diagnosis of influenza A and B virus by immunofluorescence of exfoliated nasopharyngeal cells have shown variable sensitivity (40 to 100%) and specificity (86 to 99%); they require specialist equipment and expertise and are labour intensive. Rapid, near-patient tests for influenza vary in complexity, sensitivity, and specificity. They can aid clinical management, but their value in the hospital setting in influencing prescribing and infection control is unclear. We plan to use the Quidel QuickVue influenza A and B test. It is the most rapid of the near patient tests; is particularly simple to perform; and has a median sensitivity and specificity of 80%. Its diagnostic accuracy in the elderly is unknown. Molecular diagnosis of influenza by reverse transcription PCR (RT-PCR) provides improved sensitivity and specificity, allows accurate detection, and facilitates the subtyping of influenza. Multiplex PCR has the added advantage of allowing identification of several infectious agents (e.g., influenza subtypes A/H1N1, A/H3N2, and B, and RSV types A and B) in one sample and in one reaction. The technique is used routinely within the specialist diagnostic facilities of the Health Protection Agency, Colindale, where it has a sensitivity of 92% and specificity of 84%. We plan to evaluate the ease of use and usefulness of PCR in Leicester as part of the process of distributing it more widely.

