#### 7.6 Statistical analysis

All analyses for both process and clinical outcomes will be based on Intention to Treat (ITT) analyses.

Impact of test result on prescribing The time to prescription of `narrow spectrum', `oral antibiotics' or `no antibiotics' between the three groups will be assessed using survival analysis techniques, whilst the use of neuraminidase inhibitors in those with influenza will be assessed using  $\chi^2$  tests, together with 95% CIs. Further analyses to allow for potential differences in patient demographics and baseline clinical characteristics between the three diagnostic test groups, and not allowed by stratification, will make use of cox proportional hazards regression modelling in the case of time to appropriate prescribing and logistic regression techniques in the case of neuraminidase inhibitors.

*Length of hospital stay* Length of hospital stay in the three diagnostic groups will initially be compared using non-parametric methods. Further analyses to allow for potential differences in patient demographics and baseline clinical characteristics between the three diagnostic test groups, and not allowed by stratification, will make use of generalised linear models in order to accommodate any skewness in the data.

*Mortality rates* Mortality rates between the three diagnostic testing groups will be compared by means of a Log-Rank Test and Kaplan-Meier survival curves. Adjustment for potential differences in patient demographics and baseline clinical characteristics between the three diagnostic test groups, and not allowed by stratification, will make use of Cox proportional hazards regression methods.

*Diagnostic accuracy* Sensitivity, specificity, positive predictive value of molecular and near patient diagnostic tests in comparison to traditional laboratory methods will be calculated together with 95% CIs. Heterogeneity in the sensitivity and specificity with respect to patient demographics and baseline clinical characteristics will be explored as secondary analyses using patient defined sub-groups.

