Admission to intensive care The proportions of patients in the three groups who are admitted to intensive care within the first 10 days of admission will be compared using  $\chi^2$  tests, together with 95% CIs. Further analyses to allow for potential differences in patient demographics and baseline clinical characteristics between the three diagnostic test groups, and not allowed by stratification, will make use of logistic regression techniques.

*Ventilatory support* The proportions of patients in the three groups who receive ventilatory support within the first 10 days of admission will be compared using  $\chi^2$  tests, together with 95% CIs. Further analyses to allow for potential differences in patient demographics and baseline clinical characteristics between the three diagnostic test groups, and not allowed by stratification, will make use of logistic regression techniques.

Appropriate use of isolation facilities In patients with confirmed influenza or RSV the time taken from admission to the MAU to admission to a single room (isolation cubicle) will be compared between the three diagnostic groups by means of a Log-Rank Test and Kaplan-Meier survival curves. Adjustment for potential differences in patient demographics and baseline clinical characteristics between the three diagnostic test groups, and not allowed by stratification, will make use of Cox proportional hazards regression methods.

*Quality of Life (EQ-5D)* Quality of life in the three diagnostic groups will initially be compared using non-parametric methods. Further analyses to allow for potential differences in patient demographics and baseline clinical characteristics between the three diagnostic test groups, and not allowed by stratification, will make use of generalised linear models in order to accommodate any skewness in the data.

*Speed of Tests* Time taken to receive test results in the three diagnostic groups will initially be compared using non-parametric methods. Further analyses to allow for potential differences in patient demographics and baseline clinical characteristics between the three diagnostic test groups, and not allowed by stratification, will make use of generalised linear models in order to accommodate any skewness in the data.

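### Speed of tests, milestone (d): time to a result being acted upon is given a median, non-parametric methods and GLMs, with no provision for results that are never acted upon

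*Protocol*

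**What the plan says.** Protocol section 7.5.3 item 3, repeated in the synopsis, states that speed of tests "Will be assessed in terms of the median time from specimen collection to result" reaching four milestones: (a) in the case notes, (b) on the pathology database, (c) phoned to the ward, and (d) "Being acted upon in comparison to traditional laboratory culture". The analysis population is "All patients in Groups 1, 2, and 3", and then the infected subsets.

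Section 7.6, under Speed of Tests, gives the analysis: "Time taken to receive test results in the three diagnostic groups will initially be compared using non-parametric methods". Adjusted analyses "will make use of generalised linear models in order to accommodate any skewness in the data". Neither section defines acted upon or says what happens to a result on which nobody acts.

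The same section treats comparable times differently. Times to narrow-spectrum, oral and no antibiotics "between the three groups will be assessed using survival analysis techniques". Time to a single room "will be compared between the three diagnostic groups by means of a Log-Rank Test and Kaplan-Meier survival curves".

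On the speed of culture, section 1.6 says that isolation of influenza virus may take a week or longer ("a median of 8 days in one recent study").

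**The concern.** Milestones (a) and (b) are properties of the laboratory and its reporting chain. Milestone (d) is an event in patient care that may never occur. The result may call for no change, or the patient may have left hospital or died before it arrives. Such a result has no time to action.

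A GLM fitted to times cannot use a patient without a time, and a simple median ignores that patient. The loss is unequal between groups. Rapid results come back while nearly everyone is still in hospital. A viral culture result at about 8 days often does not, and those that do arrive in time are the quicker cultures in the longer-stay patients. The statistic would therefore favour culture, and its main practical weakness, results too late to use, would be missing from the one speed milestone that connects a result to management. Objective 2 concerns the benefit of speed, so this milestone deserves a summary that can show the weakness.

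**Working it through.** **1. Methods side by side (section 7.6).**

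| Time | Can it fail to occur? | Method stated |
|---|---|---|
| To narrow-spectrum, oral or no antibiotics | Yes | Survival analysis, Cox |
| To single room | Yes | Log-rank, Kaplan-Meier, Cox |
| To result acted upon | Yes | Median; non-parametric methods and GLM, worded for time to receive results |

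The first two rows are the kinds of action that would make up acting on a result.

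**2. What is recorded.** Section 6.2.1 requires the times at which results became available to be entered even after discharge or death, so availability is not confined to inpatients. Actions have narrower limits: section 4.1 documents treatment for 10 days from admission and isolation status for 7.

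**3. Illustration for viral culture.** The protocol gives no expected value for speed of tests, so there is no figure to reproduce.

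Inputs from the protocol:
- Median culture time 8 days (section 1.6).
- SD of length of stay 6 days (section 7.4).
- Treatment window 10 days (section 4.1).

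Assumptions, not in the protocol:
- Culture time T is lognormal with log-SD 0.3, 0.5 or 0.7.
- Length of stay L is lognormal with mean m = 6, 8 or 10 days, so its log-variance is ln(1 + (6/m)²). T and L are independent and share one time origin.
- A rapid result has a median of 0.5 day.

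A result can be acted upon if T ≤ min(L, 10). With 400,000 draws per scenario:

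| Log-SD of T | Share in time, m = 6 / 8 / 10 | Median T among those (days) |
|---|---|---|
| 0.3 | 21% / 34% / 48% | 6.8 / 6.8 / 6.9 |
| 0.5 | 23% / 35% / 47% | 5.5 / 5.6 / 5.9 |
| 0.7 | 25% / 37% / 47% | 4.4 / 4.7 / 5.0 |

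The median over all culture results is 8.0 days in every row. For rapid results, 99% to 100% arrive in time and the median stays at 0.5 day. If only half of the in-time culture results are acted upon, the shares fall to 11% to 24% and the medians hardly move.

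**4. Is the median reached in all randomised patients?** In these nine scenarios fewer than half of culture results can reach the milestone, so it is not. This depends on the assumptions. With mean stay 11 days, log-SD 0.35, no day-10 limit and a result needed half a day before discharge, 58.1% are in time. The median is then reached if at least 0.5/0.581 = 86% of those are acted upon.

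**5. Faster conventional tests.** With an assumed median turnaround of 2 or 3 days (log-SD 0.35, mean stay 7, 9 or 11 days, half-day lead), 70% to 99% of results are in time and the median shifts by only about 0.01 to 0.2 days. Bacterial culture and Gram stain are therefore much less affected than viral culture.

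**The case against.** The strongest reply is that the protocol does not state any exclusion. It never says that the median is over observed times or that rank tests will be used. Kaplan-Meier estimation is itself non-parametric, and the analysis sentence speaks of receiving results, without naming action on them. How non-occurrence is handled could be left to a SAP. This stands in part: the loss of patients is a consequence of the stated methods and is not written into the plan. But the GLM step has no reading that keeps a result without a time, and where the authors wanted Kaplan-Meier they named it. If the sentence does not cover milestone (d), then (d) has a median and no stated analysis, which needs the same repair.

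A reader might infer three stronger things, and the documents support none of them:
- **That culture is judged only on its early, in-hospital results.** Section 6.2.1 contradicts this for availability, and nothing shows that (c) is limited to inpatients.
- **That the plan departs from the intention-to-treat principle opening section 7.6.** That would need a stated exclusion, and there is none; speed is defined for all patients in the three groups.
- **That most culture results never reach the milestone.** This rests on an assumed mean stay and spread. The 8-day figure is for viral culture alone and comes from a cited paediatric study, while Group 3 also has Gram stain, sputum culture and blood culture.

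It is also fair that the effect of results on management has its own endpoints, prescribing and isolation times, with suitable methods. Late culture results would still show there and in (a) and (b). Against a test read in 10 to 15 minutes, a shift from 8 to about 7 days would not reverse a conclusion.

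**Conclusion.** The point holds for milestone (d) only. The event need not occur, and the stated summary and methods have no place for results never acted upon, although the same section uses survival methods for the actions concerned. The direction is clear for viral culture: it would look faster than it is, so the advantage of rapid tests would be understated.

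The size cannot be fixed from the protocol. Under the assumptions shown, the apparent viral culture time falls from 8 days to between 4.4 and 6.9 days, and 52% to 79% of viral culture results drop out even if every in-time result is acted upon. The time in the rapid arms is almost unchanged. Milestones (a) to (c) are not shown to be affected. The change is worth making because it is cheap and concerns the milestone that connects test speed to care.

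**What to change.** Amend section 7.5.3 item 3, section 7.6 and the matching synopsis text:

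1. **Define acted upon**: a recorded change in antimicrobial or antiviral treatment, or in isolation status, following the result.
2. **Report the proportion of results acted upon** in each group.
3. **Analyse (d) as time-to-event in all randomised patients** by cumulative incidence, with death and discharge without action as competing events. This matches the approach already used for prescribing and isolation times.
4. **Limit follow-up to the recording windows**: treatment changes to day 10 and isolation changes to day 7 from admission. A combined curve should stop at day 7.
5. **Keep the planned median for (a) to (c).**

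Prescriptions by the GP after discharge are captured to day 28, but the questionnaire asks for the medicine and its duration, not its start date. They cannot enter the time analysis and are best reported separately.

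The cost is analysis wording and a little more analysis work. Times of results, treatment changes, discharge and death are already collected. Isolation is noted at midday each day in section 6.2.3, while the assessment schedule asks for the time of any change, so the recorded time of change should be used where it exists. The median time to action may have to be reported as not reached for culture, and in any group where fewer than half of results lead to action. The cumulative proportions would then carry the comparison.
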